4.5 Medical Records Abstraction

Objectives of this study include identifying quantitative imaging markers that best predict engraftment quality and GVHD development in allogeneic HSCT patients. To achieve this aim, we will correlate the imaging data with the need for blood product transfusion support, biopsy based measures of bone marrow donor/recipient chimerism studies and overall bone marrow cellularity, and the clinical and/or histopathological documentation of graft versus host disease.

Patient pathology records will be obtained after the 100-day follow-up period has passed and again one year post-transplant or at the time of death if the patient expires prior to then

All patients receiving HSCT have outcomes data collected for quality and program performance assessments. This data is collected for every patient until either death or lost to follow-up. The data routinely collected includes demographic data, donor match information, and outcomes of engraftment, survival, disease relapse, and development of acute and chronic GVHD.

Image Analysis

Quantitative T1 and DWI ADC maps will be computed. Regions of interests (ROIs) will be drawn on the anatomic MR images (blinded to SUV values and clinical outcome), then transferred to FLT SUV maps. We will correlate the imaging data with the histopathological data to identify the quantitative markers that best predict engraftment quality.

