2.4 Secondary Endpoints

- 2.4.1** The overall FLT-PET bone marrow signal will be defined as the average maximum FLT SUV within the vertebrae, pelvis, and bilateral femurs measured on transplant day +60. Complete donor reconstitution will be defined as chimerisms $\geq 95\%$ within the CD3 and unfractionated compartments on bone marrow biopsy/aspirate obtained on transplant day +100
- 2.4.2** The overall FLT-PET signal within host secondary lymphoid tissue will be defined as the average maximum FLT SUV within the spleen, cervical lymph nodes, axillary lymph nodes, inguinal lymph nodes, and mesenteric lymph nodes

on transplant day +25. Acute GVHD incidence will be diagnosed either clinically or preferably pathologically within any target organ by transplant day +100.

- 2.4.3** The overall FLT-PET signal within recipient secondary lymphoid tissue (average maximum FLT SUV within the spleen, cervical lymph nodes, axillary lymph nodes, inguinal lymph nodes, and mesenteric lymph nodes) and the bone marrow (average maximum FLT SUV within the vertebrae, pelvis, bilateral femurs) in autologous transplant recipients will be compared to the corresponding overall FLT-PET signals from allogeneic transplant recipients on transplant days +25 and +60.
- 2.4.4** Transfusion independence will be defined as not having received a packed red blood cell (PRBC) or platelet transfusion within the 7 days preceding the day +35 or the day +100 time point
- 2.4.5** Bone marrow cellularity will be defined in a dichotomous manner as either hypocellular or normocellular/hypercellular based on the bone marrow pathology report from the day +35 and day +100 bone marrow biopsies.
- 2.4.6** The average FLT SUV in the vertebral column will be compared to the quantitative T1 and Diffusion Weighted Imaging (DWI) signals in the vertebral column by MRI. The average FLT SUV in the pelvis will be compared to the quantitative T1 and Diffusion Weighted Imaging (DWI) signals in the pelvis by MRI. The average FLT SUV in the bilateral femurs will be compared to the quantitative T1 and Diffusion Weighted Imaging (DWI) signals in the bilateral femurs by MRI.

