8.2 Sample Size and Accrual

This is a pilot study to gather preliminary data, and the results from this study will be used to power a future larger R01. However, we will have power to detect large differences between groups as follows. For power calculation, the null hypothesis is that there will be no difference in the FLT bone marrow signal between those allograft patients demonstrating incomplete and complete donor reconstitution on their restaging marrow biopsies, and no difference in the FLT signal within secondary lymphoid tissues between patients with and without acute GVHD.

Complete Donor Reconstitution:

Considering only the 12 allogeneic patients, we will compare the mean FLT bone marrow signal between those with and without complete donor reconstitution. In general we would expect approximately 50-70% of our patients overall to achieve complete donor reconstitution in both the unfractionated and CD3 enriched compartments by transplant day +30.

Assuming equal number of patients with/without Complete Donor Reconstitution:

A sample size of 6 in each group will have 80% power to detect a probability of 0.854 that an observation in the Complete Donor Reconstitution group is less than an observation in the non-Complete Donor Reconstitution group using a Wilcoxon (Mann-Whitney) rank-sum test with a 0.100 one-sided significance level.

Assuming unequal number of patients with/without Complete Donor Reconstitution:

A total sample size of 12 will have 80% power to detect a probability of 0.87 that an observation in the Complete Donor Reconstitution group (n=7) is less than an observation in the non-Complete Donor Reconstitution group (n=5) using a Wilcoxon (Mann-Whitney) rank-sum test with a 0.100 one-sided significance level.

Graft Versus Host Disease:

Considering only the 12 allogeneic patients, we will compare the mean FLT signal within secondary lymphoid tissues in those patients who develop acute GVHD versus those who do not based on the criteria described previously. In general we would expect that approximately 30-40% of our patients will develop some degree of acute GVHD (any site and any clinical grade) by transplant day +100

A sample size of 6 in each group will have 80% power to detect a probability of 0.854 that an observation in the non-GVHD group is less than an observation in the GVHD group using a Wilcoxon (Mann-Whitney) rank-sum test with a 0.100 one-sided significance level.

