Appendix B: Reader Study Data Collection Form

Patient ID: _____

Reader: _____
Date: _____

Overall Assessment:

FLT SUV in pelvis _____

FLT SUV in vertebrae _____

FLT SUV in right femur _____

FLT SUV in left femur _____

FLT SUV in inguinal lymph nodes _____

FLT SUV in axillary lymph nodes _____

FLT SUV in cervical lymph nodes _____

FLT SUV in mesenteric lymph nodes _____

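### Section 4.5 sets out to find the best-predicting imaging markers in 12 patients, but section 8.3.1 makes no allowance for choosing among them, so the top marker will look better than it is

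*Combined protocol and SAP*

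**What the plan says.** Section 4.5 states the aim twice. Its opening speaks of "identifying quantitative imaging markers that best predict engraftment quality and GVHD development in allogeneic HSCT patients", and its Image Analysis paragraph repeats it for engraftment: the imaging results are to be set against the histopathology to "identify the quantitative markers that best predict engraftment quality".

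The candidates have to be gathered from elsewhere. Appendix B has separate entries for FLT in pelvis, right femur and left femur, as well as "FLT SUV in vertebrae". Section 4.5 computes T1 and ADC maps. Section 2.4.6 has regional FLT "compared to the quantitative T1 and Diffusion Weighted Imaging (DWI) signals in the vertebral column by MRI", and likewise in the pelvis and femurs.

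Section 8.3.1 names rank-sum tests, Spearman and Pearson coefficients and exploratory ROC analyses. It mentions no multiplicity control, internal validation or optimism correction.

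The primary engraftment comparison is separate. Section 2.3.1 pre-defines one marrow composite, and section 8.2 powers that comparison, "Considering only the 12 allogeneic patients".

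**The concern.** Looking for the best predictors means choosing among several markers. When the same few patients are used both to choose a marker and to describe its performance, the chosen marker's AUC is biased upward, even if no marker carries any information. This differs from the familiar optimism of choosing a cutoff on one marker.

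At stake is what the pilot hands on. Section 8.2 says its results will be used to power a larger study. If a selected marker's AUC were used for that, the next study could be too small or could pursue the wrong marker.

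**Working it through.** **1. The plan's own figure.** Section 8.2 states: "A sample size of 6 in each group will have 80% power to detect a probability of 0.854", "using a Wilcoxon (Mann-Whitney) rank-sum test with a 0.100 one-sided significance level". The probability in that statement is on the AUC scale. Noether's formula is N = (z_α + z_β)² / [12·c(1−c)·(p − 0.5)²]. With z_α = 1.2816, z_β = 0.8416, c = 0.5 and p = 0.854, N = 4.508 / (12 × 0.25 × 0.354²) = 11.99, and power is 80.0%. For the 7/5 case, "A total sample size of 12 will have 80% power to detect a probability of 0.87": Φ(√(12 × 12 × 7/12 × 5/12) × 0.37 − 1.2816) = Φ(0.907) = 81.8%, within 2 points. The stated power reproduces.

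**2. Candidates (an inference).** FLT at the four Appendix B marrow sites, plus T1 in three regions, plus ADC in three regions: 4 + 3 + 3 = 10 per scan. Another count also gives 10: FLT, T1 and DWI in three regions (9) plus the composite.

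**3. Level for one null marker.** At 6/6 there are C(12,6) = 924 label arrangements. The smallest U significant at one-sided 0.10 is 27 of 36, which is AUC 0.75, with exact level 0.0898. If either direction is accepted, the level per marker is 2 × 0.0898 = 0.18.

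**4. Independent-marker benchmark.** The chance that at least one of 10 independent null markers reaches 0.75 is:
- all directions fixed: 1 − 0.9102^10 = 61%
- FLT fixed, MRI free: 1 − 0.9102^4 × 0.8204^6 = 79%
- all free: 1 − 0.8204^10 = 86%

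Correlation between markers lowers these figures.

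**5. Null simulation.** Settings: 10 noise markers (4 FLT, 3 T1, 3 ADC), 12 patients split 6/6, 20,000 runs per setting. The documents give no correlations, so within-modality correlation was varied from 0.3 to 0.8, with none between modalities. Where direction is free, each marker scores max(AUC, 1 − AUC).

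| Direction | Mean best AUC | At least one ≥ 0.75 | Best ≥ 0.854 |
|---|---|---|---|
| All fixed in advance | 0.72-0.75 | 43-57% | 14-18% |
| FLT fixed, MRI free | 0.77-0.80 | 63-77% | 21-27% |
| All free | 0.79-0.82 | 71-84% | 25-33% |
| Four FLT sites only, fixed | 0.59-0.65 | not tabulated | not tabulated |

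**6. Sensitivity.** The alternative count (9 regional measures plus composite) gives almost the same means at 6/6 over the same correlations: 0.71-0.75, 0.77-0.80 and 0.79-0.81. At 7/5 that count gives 0.72-0.75, 0.78-0.80 and 0.79-0.82. With correlation 0.9 across all 10 markers, including between modalities, the direction-free mean falls to 0.73.

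**The case against.** Much of the case on the other side stands.

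- **The count and the ranking are inferred.** Section 4.5 speaks of markers in the plural and gives no list, number or single winner. Six of the ten candidates are MRI measures, and the only objective and endpoint listed for them (2.2.9 and 2.4.6) relate them to FLT, not to biopsy results. They count only if section 4.5 is read to include MRI against histopathology.
- **Direction matters.** Section 8.2 uses a one-sided test with a stated direction for the composite. A reader might infer that noise alone would give an AUC of about 0.81, close to the powered 0.854. That is the direction-free scenario and cannot stand as the single answer. Nor can 71-84% be read as the chance of a one-sided 0.10 result, since the level per marker there is about 0.18. On the other hand, no direction is stated anywhere for T1 or ADC, so free direction cannot be ruled out for those.
- **The main safeguard exists.** A reader might infer that the primary test or its power is compromised. Neither is, because each rests on one pre-defined composite. Nor does section 8.3.1 lay down a marker-by-marker test.
- **The consequence is conditional.** Section 8.2 does not say that a selected marker would supply the future effect size; the composite is the natural source.
- **It is a pilot.** Exploratory ranking is legitimate here. That does not make the top marker's AUC unbiased, and section 8.3.1 says nothing to warn of the bias.

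**Conclusion.** The concern holds as a minor point. The plan commits to finding the best-predicting markers in 12 patients and has no step that allows for the choice, so the leading marker's AUC will be optimistic. For one scan and one engraftment outcome split 6/6, with about 10 candidates and within-modality correlation of 0.3 to 0.8, the mean best AUC from noise lies between 0.72 and 0.82. A single null marker with its direction fixed averages 0.50. Where in that range the trial falls depends on how many directions are fixed beforehand, and the figure is much lower if only the four FLT sites compete. The candidate count, the correlations and the inclusion of MRI against histopathology are assumptions. The same aim is stated for GVHD, but that was not sized here.

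**What to change.** In sections 4.5 and 8.3.1:

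- List the candidate markers and the expected direction of each, and say whether T1 and ADC are to be related to histopathology.
- Report every marker's AUC with its interval, not only the leading one.
- Give the top marker a max-statistic permutation p-value: permute the outcome labels across all markers at once and compare the observed best AUC with the distribution of the best. Complete enumeration is feasible, with 924 arrangements at 6/6 and 792 at 7/5.
- Replace the best-predictor wording with 'rank for further study'.
- State that the effect size for the future study comes from the pre-defined composite in 2.3.1, not from the selected marker.

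The cost is a few lines of text and a short permutation script, with no new data or patients. The downside is that the top marker will look less impressive.

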5.0 EXPECTED RISKS/UNANTICIPATED PROBLEMS

5.1 Expected Risks

5.1.1 Risks of PET/MRI

5.1.1.1 IV Placement

For patients, study participation may require placement of an IV for administration of the radioisotope for PET/MRI scans if we are unable to utilize existing central venous access. IV placement may result in pain, bruising or infection. The IV will be placed by a certified BRIC technologist using sterile techniques to minimize the risk of bleeding and infection. Patients will have the option of a topical anesthetic for IV placement to reduce pain and discomfort.

5.1.1.2 Radiation

The FLT-PET/MRI scans will expose subjects to controlled amounts of limited radiation. Subjects will be informed of an estimated dose of radiation as specified by the Radiation Safety Committee. The amount of risk to this estimated dose will be compared to the annual radiation exposure a typical individual receives on a yearly basis from natural background radiation in the informed consent. This radiation exposure involves a small risk and is necessary to obtain the information desired.

Risks arising from the imaging procedure itself including injury to the donor bone marrow and/or additional infectious complications are felt to be extremely low but theoretically possible. Notably FLT-PET scanning has been applied to both the autologous and allogeneic stem cell transplant patient population previously with no reported adverse effects on patient outcomes.^{9,11} Furthermore an NCI study is currently ongoing which specifies the use of FLT-PET scanning in

allogeneic stem cell transplants as early as 5 days post-transplant (NCI study NCT01338987, Pilot Study of Lupron to Improve Immune Function After Allogeneic Bone Marrow Transplantation). Nevertheless, the following assessments will be undertaken to carefully monitor for any unexpected effects on peripheral blood counts or susceptibility to infection.

5.1.1.2.1 Allogeneic Transplant Patients

All allogeneic transplant recipients on study will undergo at least twice weekly complete blood count analyses and complete metabolic panels (i.e. blood chemistry including electrolytes, serum creatinine and BUN, liver function tests) during the first 90 days post-transplant. All allogeneic transplant recipients on study will also undergo weekly quantitative viral loads for CMV and EBV. Additional infectious testing will be obtained as clinically indicated. Notably, all of these evaluations are already obtained for all allogeneic stem cell transplant patients at The University of North Carolina as part of the standard of care. It is routine practice at UNC for all allogeneic transplant recipients to be seen 2-3 times weekly in the bone marrow transplant clinic over the entire first 100 days post-transplant.

5.1.1.2.2 Autologous Transplant Patients

Autologous transplant patients on study will undergo at least two complete blood count analyses and two complete metabolic panels during the week immediately following their first scan, and at least one CBC and one comprehensive metabolic panel following their second scan. Since the second scan will be obtained many weeks after count recovery, any risk to the donor bone marrow product is considered to be even less at this time point, and hence only a single set of labs is mandated. As CMV and EBV reactivation are extremely rare in the autologous transplant patients, viral loads for these agents will not be mandated. Rather, any relevant infectious work-up will be guided by the clinical circumstances.

5.1.1.3 FLT

FLT will be available through the Biomedical Research Imaging Center Radiopharmaceutical Laboratory as an investigational drug under and National Cancer Institute NCI IND. The associated risks and drug details are listed in Appendix A.

5.1.2 Patient Confidentiality

The risk of breach of confidentiality is low and will be minimized by securing all identifiable data in locked cabinets and password-protected electronic medical records. Imaging data will be de-identified during acquisition, labeled with a study ID and post-processed on secure computers.

6.0 TIME AND EVENTS TABLE

6.1 Time and Events Table

	Baseline	+25 after BMT +/- 5 days	35 days after BMT +/- 5 days	+60 days after BMT +/- 5 days	100 days after BMT +/- 5 days
Screening	X				
Informed Consent	X				
FLT-PET-MR		X		X	
Standard of Care Bone Marrow Biopsy ^a			X		X
	^a Allogeneic transplant patients only				

7.0 ADVERSE EVENTS

7.1 Definition

7.1.1 Adverse Event (AE)

An adverse event (AE) is any untoward medical occurrence (e.g., an abnormal laboratory finding, symptom, or disease temporally associated with the use of a medicinal product, in this case the FLT radiotracer) in a patient or clinical investigation subject administered a pharmaceutical product and which does not necessarily have a causal relationship with this treatment. An AE can therefore be any unfavorable and unintended sign (including an abnormal laboratory finding), symptom, or disease temporally associated with the use of a medicinal product, whether or not related to the medicinal product.

Hospitalization for elective surgery or routine clinical procedures that are not the result of an AE (e.g., surgical insertion of central line) need not be considered AEs and should not be recorded as an AE. Disease progression should not be recorded as an AE, unless it is attributable by the investigator to the study therapy.

As defined by UNC's IRB, unanticipated problems involving risks to study subjects or others (UPIRSO) refers to any incident, experience, or outcome that:

- Is unexpected (in terms of nature, severity, or frequency) given (a) the research procedures that are described in the protocol-related documents, such as the IRB-approved research protocol and informed consent

document; and (b) the characteristics of the subject population being studied;

- Is related or possibly related to a subject's participation in the research; and
- Suggests that the research places subjects or others at a greater risk of harm (including physical, psychological, economic, or social harm) related to the research than was previously known or recognized.

7.1.2 A suspected adverse reaction (SAR) is any AE for which there is a *reasonable possibility* that the drug/radiotracer is the cause. *Reasonable possibility* means that there is evidence to suggest a causal relationship between the drug/radiotracer and the AE. A suspected adverse reaction implies a lesser degree of certainty about causality than adverse reaction, which means any adverse event caused by a drug/radiotracer.

Causality assessment to a study drug/radiotracer is a medical judgment made in consideration of the following factors: temporal relationship of the AE to study drug/radiotracer exposure, known mechanism of action or side effect profile of study treatment, other recent or concomitant drug exposures, normal clinical course of the disease under investigation, and any other underlying or concurrent medical conditions. Other factors to consider in considering drug/radiotracer as the cause of the AE:

- Single occurrence of an uncommon event known to be strongly associated with drug/radiotracer exposure (e.g., angioedema, hepatic injury, Stevens-Johnson Syndrome)
- One or more occurrences of an event not commonly associated with drug/radiotracer exposure, but otherwise uncommon in the population (e.g., tendon rupture); often more than once occurrence from one or multiple studies would be needed before the investigator could determine that there is *reasonable possibility* that the drug/radiotracer caused the event.
- An aggregate analysis of specific events observed in a clinical trial that indicates the events occur more frequently in the treatment group than in a concurrent or historical control group

7.1.3 Unexpected AE or SAR

An AE or SAR is considered unexpected if the specificity or severity of it is not consistent with the applicable product information (e.g., Investigator's Brochure (IB) for an unapproved investigational product or package insert/summary of product characteristics for an approved product). Unexpected also refers to AEs or SARs that are mentioned in the IB as occurring with a class of drugs/radiotracers or as anticipated from the pharmacological properties of the drug/radiotracer, but are not specifically mentioned as occurring with the particular agent under investigation.

7.1.4 Serious AE or SAR

An AE or SAR is considered serious if, in the view of either the investigator or sponsor, it results in any of the following outcomes:

- Death;
- Is life-threatening (places the subject at immediate risk of death from the event as it occurred);
- Requires inpatient hospitalization (>24 hours) or prolongation of existing hospitalization;*
- Results in congenital anomaly/birth defect;
- Results in a persistent or significant incapacity or substantial disruption of the ability to conduct normal life functions;
- Important medical events that may not result in death, be life-threatening, or require hospitalization may be considered a serious adverse drug experience when, based upon appropriate medical judgment, they may jeopardize the patient or subject and may require medical or surgical intervention to prevent one of the outcomes listed in the definition. For reporting purposes, also consider the occurrences of pregnancy as an event which must be reported as an important medical event.

*Hospitalization for anticipated or protocol specified procedures such as administration of chemotherapy, central line insertion, metastasis interventional therapy, resection of primary tumor, or elective surgery, will not be considered serious adverse events.

Pregnancy that occurs during the study must also be reported as an SAE.

